6.1. General Considerations

Statistical analysis of this study will be the responsibility of Eli Lilly and Company (Lilly). The latest version of the Medical Dictionary for Regulatory Activities (MedDRA) will be used.

Analyses and summaries from assessment of endpoints described in the protocol (for example, described in Table AMAJ.4.1 and in Section 4 of AMAJ protocol) are planned to be included in a clinical study report (CSR). Analyses and summaries for key safety data are also planned to be included in the CSR. Results from additional efficacy analysis pre-defined below and other safety analyses may also be provided in the CSR as deemed appropriate. Any analysis or summary not included in the CSR will be available upon request.

Any change to the data analysis methods described in the protocol will require a protocol amendment **ONLY** if it changes a principal feature of the protocol. Any other change to the data analysis methods described in the protocol and the justification for making the change will be described in the CSR.

Additional exploratory analyses of the data may be conducted as deemed appropriate. Some of these additional supplementary analyses will be prespecified in a separate supplemental SAP.

Some of the analyses described in this document will be incorporated into interactive display tools instead of or in addition to static displays.

The Schedule of Activities outlined in the protocol specifies the allowable windows for assessments. Assessments performed outside these windows will not be excluded from any analysis.

6.1.1. Patient Populations for Analysis

Patient populations are defined in [Table AMAJ.6.1](#) along with the analysis they will be used to conduct. Patients will be analyzed according to the treatment to which they were assigned for all populations. [Table AMAJ.6.2](#) describes the treatment groups and the comparisons for each study period and the analysis population.

Table AMAJ.6.1. Patient Populations for Analysis

Population	Description
All Entered Patients	All patients who signed informed consent.
Intent-to-Treat (ITT) Population	All randomized patients, even if the patient does not take the assigned treatment, does not receive the correct treatment, or otherwise does not follow the protocol. Unless otherwise noted, efficacy and health outcomes analyses for the both induction period and combined induction/maintenance periods will be conducted on this population.
Induction Safety	All randomized patients who received at least 1 dose of study treatment . Safety analyses for the induction period will be conducted on this population.
All Active Treatment Safety	All randomized patients who received at least 1 dose of mirikizumab or secukinumab .
Induction PPS	All randomized patients who do not have important protocol deviations excluded from per protocol analysis (IPDPP) in the induction period. IPDPP are described in a separate document referred to as the “The AMAJ Trial Issues Management Plan”. These patients will be used to reanalyze the primary endpoints only.
Induction and Maintenance PPS	All randomized patients who do not have IPDPP in the combined induction/maintenance periods. IPDPP are described in a separate document referred to as the “The AMAJ Trial Issues Management Plan.” These patients will be used to reanalyze the selected major secondary endpoints of PASI 90 and sPGA (0,1) at Week 52.

Abbreviations: PASI = Psoriasis Area and Severity Index; PASI 90 = $\geq 90\%$ improvement in PASI from baseline; PPS = per protocol set; sPGA = static Physician’s Global Assessment.

Table AMAJ.6.2. Treatment Groups and Comparisons for Each Study Period and Analysis Population

Study Period	Analysis Population	Treatment Groups	Inferential Comparisons
Induction Period	ITT; Induction Safety; Induction PPS	placebo Q4W; 300 secu; 250 miri Q4W	300 secu vs placebo Q4W; 250 miri Q4W vs placebo Q4W; 250 miri Q4W vs 300 secu
Induction and Maintenance Periods*	ITT; Induction and Maintenance PPS	placebo/250 miri; 300 secu; 250 miri Q4W/125 miri Q8W; 250 miri Q4W/250 miri Q8W; Total miri/miri (Note: Total miri represents the combined treatments of 250 miri Q4W/125 miri Q8W and 250 miri Q4W/250 miri Q8W.)	250 miri Q4W/125 miri Q8W vs 300 secu; 250 miri Q4W/250 miri Q8W vs 300 secu (For efficacy/healthoutcome measures, the comparisons will be only conducted from Week 20 to Week 52)
All Active Treatment Periods	All Active Treatments Safety	placebo/250 miri; 300 secu; 250 miri Q4W/125 miri Q8W; 250 miri Q4W/250 miri Q8W; all miri (Note: all miri represents the combined treatments of placebo/250 miri, 250 miri Q4W/125 miri Q8W and 250 miri Q4W/250 miri Q8W.)	250 miri Q4W/125 miri Q8W vs 300 secu; 250 miri Q4W/250 miri Q8W vs 300 secu

Treatment Groups and Comparisons for Each Study Period and Analysis Population

Study Period	Analysis Population	Treatment Groups	Inferential Comparisons
All Active Treatment + Follow-up Periods	All Active Treatment Safety	300 secu + FUP; all miri + FUP (Note: the header with “+ FUP” is used to emphasize that the observations from Follow-up Period are included.)	
All Periods	ITT	For study disposition only: placebo/250 miri; 300 secu; 250 miri Q4W/125 miri Q8W; 250 miri Q4W/250 miri Q8W; Total miri/miri	
	Induction Safety Population	For hepatic plot only: Ever on miri; Never on miri	

Abbreviations: FUP = follow-up; ITT = intent-to-treat; miri = mirikizumab; PPS = per protocol set; Q4W = every 4 weeks; Q8W = every 8 weeks; secu = secukinumab.

* For some analyses based on response status at certain weeks (Week 16 or 24), only maintenance period will be used, and the placebo/250 miri treatment group might not be displayed.

Note: for immunogenicity analysis, 300 secu treatment group will be excluded, thus the comparisons involving 300 secu will not be conducted; also the outputs for the “All Active Treatment Period” and “All Active Treatment + Follow-up Periods” will be combined.

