Induction and Maintenance Periods	Use the definition of the start of the Induction Period.	Use the definition of the end of Maintenance Period.
Follow-up Period: All patients who had Visit 801 or 802 are considered to have entered the Follow-up Period.	The latest of the following dates: (1) after the end of the Induction Period as described above, (2) after the end of the Maintenance Period as described above	The last date of the last study visit and study disposition date
All Active Treatment Periods: All patients who are treated with mirikizumab or secukinumab are considered to have entered this period.	For mirikizumab and secukinumab induction treatment groups, use the definition of the start of Induction Period; For placebo/250 miri treatment group, use the definition of the start of Maintenance Period.	The latest of the following dates: (1) the end of the Induction Period, (2) the end of the Maintenance Period
All Periods (Induction + Maintenance + Follow-up Periods)	Induction period start date	The last date of the last study visit and study disposition date

^a Missing dose time will be imputed as the earliest time that is consistent with available data about dose time. For example, suppose the minutes are missing but hour is present; in this case, we would impute the minutes to be 0.

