6.14. Safety Analyses

The planned analyses of safety data will be performed with an intent to maintain consistency with compound level standard safety analyses. These standards are based on internal standards which were informed by Clinical Data Interchange Standards Consortium (CDISC) standards, regulatory guidance (for example, FDA Clinical Review Template), and cross-industry standardization efforts (for example, Pharmaceutical Users Software Exchange [PhUSE] white papers from the Standard Analyses and Code Sharing Working Group provided in the PhUSE Computational Science Deliverables Catalog [WWW]).

In general, safety evaluations will be based upon the following safety analysis populations with their associated study periods:

- Induction Safety Population
- All Active Treatment Safety Population

These analysis populations are fully defined in [Table AMAJ.6.1](#), while [Table AMAJ.6.2](#) describes the treatment groups, associated study periods and the comparisons for each analysis population.

Unless otherwise noted, Fisher's exact test will primarily be used to compare percentages, and odds ratios will be provided. Odds ratios will be created with mirikizumab treatment as the numerator, and placebo or secukinumab as the denominator.

Treatment differences in mean change for continuous measurements will be assessed using an ANCOVA model containing terms for treatment and the continuous covariate of baseline measurement. Type 3 sums of squares will be used. The significance of within-treatment group changes from baseline will be evaluated by testing whether the treatment group LS mean changes from baseline are different from zero using a t-statistic.

Not all displays described in this section will necessarily be included in the CSRs. Any display described and not provided in the CSR would be available upon request. Not all displays will necessarily be created as a "static" display. Some may be incorporated into interactive display tools instead of or in addition to a static display. Any display created interactively will be included in the CSR if deemed relevant to the discussion.

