6.14.2. Adverse Events

A treatment-emergent adverse event (TEAE) is defined as an event that first occurred or worsened in severity after baseline. The MedDRA Lowest Level Term (LLT) will be used in the treatment-emergent computation. The maximum severity for each LLT during the baseline period will be used as baseline. The treatment period will be included as postbaseline for the analysis. For events with a missing severity during the baseline period, it will be treated as ‘mild’ in severity for determining treatment-emergence. Events with a missing severity during the postbaseline period will be treated as ‘severe’ and treatment-emergence will be determined by comparing to baseline severity. For events occurring on the day of first taking study medication, the start times of the study treatment and AE will be used to determine whether the event was pre- versus posttreatment. If start time for the AE is missing, it will be assumed to have started in the later period.

Summary tables as described in [Table AMAJ.6.7](#) will be presented for the 2 safety populations/periods as indicated. Summary tables will include the number and percentage of patients reporting an event. For events that are gender-specific (as defined by MedDRA), the number of participants at risk will include only patients from the given gender. Comparisons will be performed using Fisher’s exact test. For document writing purposes, tests with 2-sided p-values less than 0.05 will be referred to as “having strong evidence for a treatment difference”, unless otherwise noted. However, p-values should not be over interpreted for these safety analyses. Except for prespecified hypotheses, they correspond to data-driven hypotheses and hence are only useful as a flagging mechanism.

For the 2 safety populations, the baseline period and postbaseline will be defined as follows:

- *Induction Safety Population*: The baseline period is the Screening Period. The postbaseline period will be the Induction Period.
- *All Active Treatment Safety Population*: The baseline period for patients randomized to mirikizumab and secukinumab during induction is the Screening Period. For patients randomized to placebo, the baseline events are those events which are ongoing at the time of the first injection with mirikizumab (that is, the baseline period is a moment in time). Two different postbaseline periods will be used:
 - For “all miri” and “all secu”, the All Active Treatment Periods will be used.

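### SAP 6.1.1 groups safety data by assigned treatment, so induction events after mirikizumab given in error to a placebo patient count under placebo and in no mirikizumab column

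*SAP*

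**What the plan says.** SAP 6.1.1, introducing Table AMAJ.6.1, sets one grouping rule: "Patients will be analyzed according to the treatment to which they were assigned for all populations". The table includes both safety sets. Induction Safety takes randomized patients "who received at least 1 dose of study treatment". All Active Treatment Safety takes randomized patients "who received at least 1 dose of mirikizumab or secukinumab". Receipt of a dose therefore decides who enters a safety set, and assignment decides the column. The ITT row of the same table foresees a patient who "does not receive the correct treatment".

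SAP 6.14 sends the safety work back to these definitions: "In general, safety evaluations will be based upon the following safety analysis populations with their associated study periods". Neither 6.14 nor its subsections on adverse events, laboratory values and special topics gives an as-received rule.

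Two timing rules matter for placebo-assigned patients in the All Active set:

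- Table AMAJ.6.3, start of the active period: "For placebo/250 miri treatment group, use the definition of the start of Maintenance Period".
- SAP 6.14.2, baseline: "the baseline events are those events which are ongoing at the time of the first injection with mirikizumab".

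One display is labelled differently. Table AMAJ.6.2 has "For hepatic plot only: Ever on miri; Never on miri".

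**The concern.** Grouping by assignment protects the randomised comparison for efficacy. A safety table answers another question: what happened to people after the drug they were actually given. If a placebo-assigned patient receives active drug and has an event, counting it under placebo raises the comparator's rate. For an active-versus-placebo contrast that narrows the apparent risk, which is the unsafe direction. The placebo arm is one eighth the size of the pooled mirikizumab arm, so each such event carries more weight there.

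The two timing rules also fail to meet for this patient. The planned switch from placebo to mirikizumab is at Week 16, where baseline and start of counting coincide. After an earlier dose given in error they separate, and the SAP does not say where the events between them belong.

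**Working it through.** **1. The rules applied to one patient.** Take a placebo-assigned patient given mirikizumab in error at Week 4, with a new adverse event between Week 4 and Week 16.

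- Induction Safety tables: the patient was dosed, so is in the set, and is grouped as assigned (6.1.1). The event counts under placebo.
- All Active Treatment Safety, membership: one mirikizumab dose qualifies the patient (Table AMAJ.6.1).
- All Active, baseline: events ongoing at the first mirikizumab injection, here Week 4 (6.14.2). The event began later, so it is not a baseline event.
- All Active, postbaseline: the period starts at Maintenance, normally Week 16 (Table AMAJ.6.3). The event began earlier, so it is not a postbaseline event.
- Result: the event is in the placebo column of the induction tables and in no mirikizumab column.

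Laboratory values follow the same path. SAP 6.14.3 takes the placebo patient's baseline before the first mirikizumab treatment and reuses the 6.14.2 postbaseline periods.

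If the patient stops before Week 16, Maintenance never starts. SAP 6.14.1 defines All Active exposure for placebo-assigned patients only if they enter Maintenance. The patient is then in the set with no defined exposure time.

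**2. Arm sizes (SAP 5.2).** 1443 patients at 4:4:4:1.

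- 1443 × 4/13 = 444 in each active arm, and 1443 × 1/13 = 111 on placebo.
- Pooled mirikizumab in induction: 444 + 444 = 888.

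These match the SAP's stated sizes.

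**3. Weight of one event.**

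- Placebo: 1/111 = 0.90 percentage points.
- One 444-patient arm: 1/444 = 0.23 points.
- Pooled mirikizumab: 1/888 = 0.11 points.

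The ratio of placebo to pooled mirikizumab is 888/111 = 8.

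**4. Expected shift.** Let m be the share of placebo-assigned patients misdosed with active drug, and p0 and p1 the placebo and active event rates. The as-assigned placebo rate is p0(1 − m) + p1·m, so the observed difference is (p1 − p0)(1 − m), a loss of m(p1 − p0). The documents give none of these values. Assume p0 = 5% and p1 = 10%, a true difference of 5.00 points:

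| Assumed m | Observed difference (points) | Loss (points) |
|---|---|---|
| 0.5% | 4.98 | 0.02 |
| 1% | 4.95 | 0.05 |
| 2% | 4.90 | 0.10 |
| 5% | 4.75 | 0.25 |

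For a rare event with an assumed 1% active rate, a placebo rate near zero and m = 2%, the expected loss is 0.02 × 1 = 0.02 points.

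**The case against.** The strongest reply is that membership by receipt and grouping by assignment are coherent for the trial as planned. The baseline wording in 6.14.2 was written for the Week 16 switch, and the gap appears only when it is applied to an unplanned error. That is a fair account of how the gap arose. It does not close it, because the SAP itself foresees patients who receive the wrong treatment.

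Several limits on the size and reach of the point stand:

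- **Size.** A reader might infer a distortion of about 2 points on a rare serious event: 2% of 111 is about 2 patients, and 2/111 = 1.8 points. That would require every misdosed patient to have the event, and the 2% is an assumption. The documents support neither.
- **Lost events.** A reader might infer that the events vanish. They do not. They appear in the induction tables; serious ones appear in the SAE listing for the ITT population (Table AMAJ.6.7); and important protocol deviations are listed by patient (6.18). None of these moves an event to the drug received.
- **Dose groups.** A reader might infer that a 125/250-mg mix-up undermines a dose comparison. No inferential comparison between the two doses is planned (Table AMAJ.6.2), both arms receive 250 mg in induction, and the pooled mirikizumab column is unaffected. Only the maintenance dose columns, and each dose's comparison with secukinumab, could be touched.
- **Direction.** Narrowing toward no difference applies to active/placebo errors. For a mirikizumab/secukinumab error the direction depends on which drug has the higher event rate.
- **Likelihood.** Cartons are confirmed in the IWRS (5.3), which makes misdosing less likely.
- **Use of p-values.** SAP 6.14.2 treats safety p-values as a flagging device, so no confirmatory conclusion rests on this rule.

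The compound level safety standards, the Trial Issues Management Plan and the main protocol are not among the documents reviewed and may say more. If any of them groups by treatment received, it would conflict with the sentence in 6.1.1, which would still need changing.

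**Conclusion.** The point holds as a defect in a stated rule. The as-assigned sentence covers both safety sets, nothing in the SAP's safety sections overrides it, and the rules for baseline and start of counting leave events after an erroneous mirikizumab dose in induction outside every mirikizumab column until Maintenance begins.

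The effect is conditional on misdosing, whose rate is unknown. One event is worth 0.9 points in the placebo column, while the expected shift is about 0.1 point under assumed rates of 5% and 10% with 2% misdosing. This matters mainly for reading individual rare events, where a single case in a small placebo arm is visible.

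It would go too far to say that every safety display ignores exposure: the hepatic plot's ever/never labels read as exposure-based and may be an exception. Cohort 2 of the Japan addendum has a single assigned treatment, so misattribution between arms cannot arise there.

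**What to change.** 1. In SAP 6.1.1, limit the as-assigned sentence to the ITT and per-protocol sets.
2. For the two safety sets, place each patient in one column per period by treatment actually received. A placebo-assigned patient who received any active dose in induction goes in that drug's column for the whole Induction Period. Moving the patient from the date of the dose instead would put one person in two columns that Fisher's exact test treats as independent.
3. In Table AMAJ.6.3, start that patient's All Active Treatment Period at the first active dose. For mirikizumab this matches the baseline in 6.14.2. If the wrong drug was secukinumab, the 6.14.2 wording, which names only mirikizumab, must be widened to match. Align the exposure rule in 6.14.1 so that a patient who stops before Maintenance has defined exposure.
4. List every patient whose received and assigned treatment differ, with dose dates and adverse events. Include strength mix-ups and patients who received more than one active drug. A rule based on the regimen received at most visits would leave a patient with a single wrong-strength dose in the assigned column, so the listing is needed to make such cases visible.

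At minimum, keep the as-assigned tables and add an as-received sensitivity table and this listing. Either version should be settled before the study team is unblinded, since later reassignment of individual events would look data-driven.

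The cost is a few lines of SAP text and an actual-treatment variable derived from dispensing and exposure records. SAP 6.9 names an IWRS dispensing dataset and an exposure form that records whether a dose was given; whether these identify the product injected must be confirmed. A few patients may sit in different columns in the safety and efficacy tables. Events before the wrong dose in the same period will also count under the active drug, and the dose dates in the listing let a reader separate them.

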6.1.1.1. Study Time Intervals

[Table AMAJ.6.3](#) displays a list of study periods along with the definition of which patients will be considered to have entered the study period and when the individuals start and end the study period. The table shows both a date and a time.

To calculate the length of any time interval or time period in this study the following formula will be used:

$$\text{Length of interval (days)} = \text{End Date} - \text{Interval Start Date} + 1$$

Only for the purpose of calculating the length of study period time intervals, the words “prior to” in [Table AMAJ.6.3](#) should be understood to mean “the day before” while the words “after” should be understood to mean “the day after.”

To convert any time length from days to years, the following formula will be used:

$$\text{Length of interval (years)} = \text{Length of interval (days)} / 365.25$$

To convert any time length from days to weeks, the following formula will be used:

$$\text{Length of interval (weeks)} = \text{Length of interval (days)} / 7$$

Table AMAJ.6.3. Definition of Study Period Time Intervals

Study Period	Start Definition	End Definition
Screening: All patients who sign informed consent are considered as entering the Screening Period.	Informed consent date	Prior to the start of induction
Induction Period: All patients who are randomized to the study are considered as entering the Induction Period.	At the first injection following randomization date/time ^a . For patients who are randomized but not dosed, the Induction Period starts on the date of randomization.	Prior to the start of maintenance. For patients who discontinue before or on the Week 16 visit, the induction period ends at the last date of treatment discontinued date or last treatment visit date.
Maintenance Period: All patients who had any Week 16 to Week 52 visits (except the ones who discontinued the study at Week 16) are considered to have entered the Maintenance Period.	At the Week 16 dosing date/time. ^a If a patient is unable to be dosed at the Week 16 visit, the Maintenance Period starts at the Week 16 visit. If the patient misses the Week 16 visit, the Maintenance Period starts at Day 118.	After the Week 52 visit date. If patients discontinued prior to Week 52, the Maintenance Period ends at the last date of treatment discontinued or last treatment visit date.
Induction and Maintenance Periods	Use the definition of the start of the Induction Period.	Use the definition of the end of Maintenance Period.
Follow-up Period: All patients who had Visit 801 or 802 are considered to have entered the Follow-up Period.	The latest of the following dates: (1) after the end of the Induction Period as described above, (2) after the end of the Maintenance Period as described above	The last date of the last study visit and study disposition date
All Active Treatment Periods: All patients who are treated with mirikizumab or secukinumab are considered to have entered this period.	For mirikizumab and secukinumab induction treatment groups, use the definition of the start of Induction Period; For placebo/250 miri treatment group, use the definition of the start of Maintenance Period.	The latest of the following dates: (1) the end of the Induction Period, (2) the end of the Maintenance Period
All Periods (Induction + Maintenance + Follow-up Periods)	Induction period start date	The last date of the last study visit and study disposition date

^a Missing dose time will be imputed as the earliest time that is consistent with available data about dose time. For example, suppose the minutes are missing but hour is present; in this case, we would impute the minutes to be 0.

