5.1.3. Blinded Maintenance Period (Week 16 to Week 52 [36 Weeks])

Patients who were randomly assigned at baseline to receive mirikizumab in the Blinded Induction Period were also randomly assigned to receive either 250-mg mirikizumab every 8 weeks (Q8W) SC or 125-mg mirikizumab Q8W SC in the Blinded Maintenance Period, with maintenance dosing starting at Week 16 and ending at Week 48. Patients who were randomized to placebo in the Blinded Induction Period will receive 250-mg mirikizumab SC every 4 weeks (Q4W) for Weeks 16 through 32 and 250-mg mirikizumab Q8W thereafter. Patients who were randomized to 300-mg secukinumab SC in the Blinded Induction Period will continue this treatment with Q4W dosing during the Blinded Maintenance Period, starting at Week 16 and ending at Week 48.

Throughout the study, patients will receive placebo, as appropriate, to maintain the study blind across treatment groups.

A discontinuation criterion has been included for patients in any treatment group who remain at or above their baseline static Physician's Global Assessment (sPGA) score at Week 16 (Visit 9) and Week 24 (Visit 11), or remain at or above their baseline Psoriasis Area and Severity Index

(PASI) score at Week 16 (Visit 9) and Week 24 (Visit 11), to ensure patients who have not shown any benefit from study treatment are offered alternative therapies.

At Week 52, patients have 1 of the following options:

- Enter Study I6T-MC-AMAH (AMAH), a long-term extension study in which patients receive 250-mg mirikizumab Q8W SC or 125-mg mirikizumab Q8W SC, OR
- Discontinue study treatment and complete Study AMAJ's 12-week Posttreatment Follow-Up Period.

[figure not shown]
Patients who discontinue early from the study for any reason during this period will stop treatment and continue to the ETV and then the 12-week Posttreatment Follow-Up Period.

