6.7. Patient Disposition

Subject flow will be summarized for the number of patient who: entered, failed screening, were randomized to each treatment, completed induction, and completed the maintenance period. Of the treatment completers, the number who enter Study AMAH, complete the posttreatment follow up, or discontinue the study will be summarized.

More specifically, the following summaries will be produced. The screen failures and reasons for screen failure will be summarized. The *treatment disposition* will be summarized for the intent-to-treat (ITT) population, with patients who entered the Maintenance Period (Table AMAJ.6.3) to be considered to have completed the Induction Period. Summaries will be by treatment group (Table AMAJ.6.2). Summaries will also include reasons for discontinuation from the study tabulated by treatment group. The *study disposition* of all patients who were randomized (that is, ITT population) will be summarized along with the reasons for discontinuation. The completers will be categorized into those completers who entered Study AMAH and those who did not.

All patients who were randomized (that is, in the ITT population) and discontinued from study treatment during any period from the study will be listed, and the timing of discontinuation from the study will be reported. If known, a reason for their discontinuation will be given.

Patient allocation by region, country, and center/site will be summarized with number of patients who entered the study, number of ITT patients for each treatment group, number of patients discontinued from study treatment, and number of patients discontinued from the study.

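### Table AMAJ.6.3 also puts a reaction to a placebo patient's first mirikizumab injection in the placebo induction column when the patient stops on the Week 16 date

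*SAP*

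**What the plan says.** All references are to the SAP.

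- **First mirikizumab dose in the placebo arm.** Section 5.1.3 says that patients "randomized to placebo in the Blinded Induction Period will receive 250-mg mirikizumab SC every 4 weeks (Q4W) for Weeks 16 through 32". The Week 16 injection is therefore their first exposure to the drug.
- **Usual boundary.** In Table AMAJ.6.3 (Section 6.1.1.1), Maintenance starts "At the Week 16 dosing date/time", and Induction ends just before that. A footnote imputes missing dose times, so the boundary can always be placed within the day.
- **Exception, Induction row.** "For patients who discontinue before or on the Week 16 visit, the induction period ends at the last date of treatment discontinued date"; the final on-treatment visit is the alternative. No clock time is given, and patients already injected that day are not treated differently.
- **Exception, Maintenance row.** Entry is open to anyone with a visit from Week 16 to Week 52, "except the ones who discontinued the study at Week 16) are considered to have entered the Maintenance Period". Whether the patient was dosed at Week 16 plays no part.
- **Safety window and label.** For the Induction Safety Population, Section 6.14.2 says "The postbaseline period will be the Induction Period". Section 6.1.1 adds: "Patients will be analyzed according to the treatment to which they were assigned for all populations". In Table AMAJ.6.2 the induction column for this arm is placebo Q4W.
- **All Active tables.** Table AMAJ.6.3 admits every patient treated with mirikizumab or secukinumab. For the placebo/250 miri group it borrows the start of Maintenance. Section 6.14.1, however, gives placebo patients All Active exposure only if they went on into Maintenance.

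**The concern.** The plan clearly means to split Week 16 at the injection. A placebo patient who reacts and continues has the event placed after Induction, where it belongs. A placebo patient with the same reaction who stops that day has it placed in Induction. Attribution therefore turns on whether the patient stopped, and the reaction itself may be the reason for stopping.

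The induction tables are the only placebo-controlled safety comparison; the All Active comparisons in Table AMAJ.6.2 are against secukinumab. The outcomes at risk are those that a first injection can trigger on the day: immediate hypersensitivity (Section 6.14.7.3), injection site reactions (Section 6.14.7.4) and AEs leading to discontinuation of treatment (Section 6.14.2.2). Counts there may be low and the placebo arm is small, so a single misplaced event is visible.

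**Working it through.** The plan gives no figure for this boundary, so there is none to reproduce. The check is to trace one patient through the rules and then weigh one event.

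**Trace.** A placebo patient is injected at Week 16, reacts and stops on that date.

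1. Entry to Maintenance: no, because the patient discontinued at Week 16.
2. End of Induction: the Week 16 calendar date. The usual rule, which closes Induction before Maintenance starts, has nothing to act on.
3. The reaction lies after baseline and on or before that date, so it is inside the Induction Period.
4. Label: placebo Q4W, as assigned. The reaction is a placebo TEAE.
5. All Active: the patient has received mirikizumab and so qualifies. The start is the Week 16 dosing time. The end is the later of the Induction and Maintenance ends, here the Week 16 date. The same reaction is counted under placebo/250 miri and all miri.
6. All Active exposure under Section 6.14.1: none, because the patient did not enter Maintenance. By the interval formula in Section 6.1.1.1 (end − start + 1), a patient who did enter would contribute 1 day, or 1/365.25 = 0.003 patient-years.

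**Does the clock-time rule in Section 6.14.2 help?** It separates events before and after treatment on the day study medication is first taken. For a placebo patient in the induction analysis that is the Week 0 dosing day. It does not shorten Induction at Week 16.

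**Weight of one event.** Section 5.2 plans 888 mirikizumab and 111 placebo patients. This agrees with the 4:4:4:1 ratio: 1443 × 8/13 = 888 and 1443 × 1/13 = 111.

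- Placebo: 1/111 = 0.90%
- Mirikizumab: 1/888 = 0.11%

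For k = 1, 2 or 3 such patients (assumed range), the placebo column gains 0.90%, 1.80% or 2.70%.

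**Illustration.** Section 6.14 uses Fisher's exact test and odds ratios with mirikizumab as the numerator. The documents give no event rates, so the mirikizumab counts below are assumptions, and placebo is taken to have no other events of the kind.

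| Mirikizumab events (assumed) | k = 0 | k = 1 | k = 2 | k = 3 |
|---|---|---|---|---|
| 4/888 (0.45%) | OR infinite, p = 1.00 | OR 0.50, p = 0.45 | OR 0.25, p = 0.14 | OR 0.16, p = 0.03 |
| 9/888 (1.01%) | OR infinite, p = 0.61 | OR 1.13, p = 1.00 | OR 0.56, p = 0.35 | OR 0.37, p = 0.14 |
| 18/888 (2.03%) | OR infinite, p = 0.25 | OR 2.28, p = 0.71 | OR 1.13, p = 1.00 | OR 0.74, p = 0.72 |

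One misplaced event can change the direction of the odds ratio only when the mirikizumab count is very low. Across the table, p falls below 0.05 only with three such patients against 4/888.

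**The case against.** **The wording allows another reading.** The Induction row speaks of patients who discontinue and looks to the treatment stop date. The Maintenance row speaks of patients who discontinued the study. Someone who stops treatment still has an early termination visit and 12 weeks of follow-up, so it can be argued that this person has not left the study at Week 16. On that view the patient enters Maintenance at the injection, and the usual rule closes Induction before the reaction. Two things weaken this. Sections 5.1.2 and 5.1.3 use discontinuing the study for exactly those patients who stop treatment and move to follow-up. And the specific Induction rule still runs to the end of the Week 16 date, so the two periods would overlap that day. The rows need aligning on either reading.

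**The event is not lost.** This stands. It also appears under mirikizumab in the All Active tables, SAEs are listed by patient, and discontinuations are listed with their timing. A reader might infer that the rule hides a mirikizumab reaction, but the documents support only double counting, with about a day of exposure missing.

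**The effect is probably small.** This stands too. The documents do not say how many patients will be dosed and stop on the same date, and the number may be zero. A reader might infer that the placebo comparison would be reversed. That depends on assumed counts, and Section 6.14.2 itself treats safety p-values as flags only.

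**Two extensions are tempting but not supported.** First, Maintenance also closes on a date at Week 52, and a reader might infer the same fault for patients moving to Study AMAH. The documents do not say when dosing in that study starts. Second, Section 6.7 takes "patients who entered the Maintenance Period (Table AMAJ.6.3) to be considered to have completed the Induction Period", so a patient who leaves at Week 16 is not an induction completer. That is an explicit convention applied alike to every arm, and it changes no efficacy or safety result.

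**Conclusion.** The point holds, as a minor one. Read literally, Table AMAJ.6.3 assigns a post-mirikizumab event to the placebo Q4W induction column for one narrow group: placebo patients who are injected at Week 16 and stop on that same date. Placebo patients who continue, or who stop before the injection, are handled correctly. Patients already on mirikizumab or secukinumab receive the same drug on both sides of the boundary.

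Each such event adds 0.90 percentage points to the planned placebo arm of 111, against 0.11 points per event among 888 on mirikizumab. It matters only for rare outcomes. The conclusion rests on the text of the table and on no assumed rate; the illustrative odds ratios and p-values do rest on assumed counts. Efficacy results are not affected.

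**What to change.** Make three changes to the SAP before unblinding:

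1. In Table AMAJ.6.3, state that any patient dosed at Week 16 leaves Induction and enters Maintenance at that injection's date and time, even if treatment stops the same day.
2. In both the Induction and Maintenance rows, limit the exception for stopping at Week 16 to patients who had no Week 16 injection, and use the same term for discontinuation in both.
3. Align Section 6.14.1 so that these patients contribute All Active exposure from the Week 16 injection.

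The event then leaves the placebo Q4W column (k/111 becomes 0/111 for events of this kind) and is counted only under placebo/250 miri and all miri, with matching exposure. Section 6.7 needs no rewording: under its own convention these few patients would count as having completed Induction.

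The cost is a few sentences and a small change to the period derivation, using dosing times that the plan already applies to other patients. No dose, visit or efficacy analysis changes.
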